10.5. Electrocardiogram Results

Electrocardiogram (ECG) results (heart rate, PR, QRS, QT, and corrected QT interval by Fredericia (QTcF) will be summarized descriptively. Descriptive statistics (sample size, mean, standard deviation, median, Q1, Q3, minimum and maximum) of baseline, post-baseline, and change from baseline values for each parameter will be provided by treatment group for all scheduled time points.

Additionally, summaries (number and percentage of subjects) of shifts in the investigator's ECG assessment from baseline (normal, abnormal and clinically significant, or abnormal but not clinically significant) to post-baseline (normal, abnormal and clinically significant, or abnormal but not clinically significant) at each scheduled post-baseline visit will be provided by treatment group.

Summaries of ECG data will be provided for the SAF analysis set. No inferential statistics will be generated. ECG data will also be listed.

Corrections to QT intervals will be made by Fridercia's method. Categorical analysis will be done consistent with ICH E14, "Clinical evaluation of QT/QTc interval prolongation and proarrhythmic potential for non-antiarrhythmic drugs" (October 2005). Subjects will be categorized and summarized according to:

- Absolute QTc interval prolongation:
 - QTc interval > 450
 - QTc interval > 480
 - QTc interval > 500
- Change from baseline in QTc interval:
 - QTc interval increases from baseline > 30
 - QTc interval increases from baseline > 60

10.6. Other Safety Data

Data listings will be provided for the following:

- Eligibility criteria
- Procedures
- Physical examination
- Pregnancy test
- Liver imaging
- Liver biopsy
- Receptor occupancy
- Pro-inflammatory biomarker multiplex
- Gene expression
- Immunoglobulins (IgM, IgA)
- Serum complement
- Viral serology
- QuantiFERON-TB Gold

11. PHARMACOKINETIC ANALYSES

Serum concentration data will be summarized descriptively for each nominal time point. Individual serum concentration-time plots will be presented on linear and semi-log scales. The PK analysis will be divided into 2 sections: primary analysis and OLE analysis, where the OLE analysis will contain individuals in the OLE population only. For descriptive statistics and mean figures, concentrations that are below the limit of quantitation (BLQ) will be treated as zero, except when an individual BLQ falls between 2 quantifiable values, in which case it will be treated as missing data and will be excluded from the mean profile.

Serum RVT-1401 concentration-time data will be analyzed by non-compartmental analysis (NCA), using actual sampling times recorded during study. The pharmacokinetic analysis and generation of tables, listings, and figures will be performed using a validated installation of Phoenix WinNonlin® version 8.1 and above (Certara, Princeton, NJ, USA) as part of a 21 CFR Part 11 compliant database system (Phoenix Knowledgebase Server “PKS”) and all the analysis will be stored on the PKS, with an audit trail for all the steps capturing the changes needed for the completion of the analysis and generation of the tables, listings, and figures.

The primary analysis of PK will be conducted on the Pharmacokinetic (PK) population, which includes all subjects who had both a pre-dose and at least 1 analyzable post-dose PK sample. The primary pharmacokinetic parameters to be calculated are area under the concentration-time curve from time zero to time AUC_{0-t} , maximum serum concentration (C_{max}), concentration at end of dosing interval (C_{trough}), and time to maximum serum concentration (t_{max}) after the first and last dose on Week 1 and Week 6, respectively. The C_{max} , t_{max} , AUC_{0-t} will be estimated using linear-up log-down method, as data permits. Additionally, C_{trough} will be determined for every dosing interval (Week 2, Week 3, Week 4, and Week 5), where PK samples taken within 8 hours before the next dose administration will be considered for reporting. Additional PK parameters (e.g. accumulation ratio for both C_{max} and/or $AUC_{(0-t)}$ between Week 1 and Week 6) may be calculated if data permits.

Pharmacokinetic (PK) parameters (AUC_{0-t} , C_{max} , C_{trough} and t_{max}) will be summarized descriptively as follows:

- Serum concentration data: sample size, number and percentage BLQ, mean, standard deviation, CV, median, minimum and maximum
- AUC_{0-t} , C_{trough} and C_{max} : sample size, mean, standard deviation, CV, geometric mean, geometric CV, median, minimum and maximum
- t_{max} : sample size, median, minimum and maximum

Summaries of PK parameters and serum concentration data will be provided for the PK analysis population. No inferential statistics will be generated. Individual and summary PK parameter and serum concentration data will also be listed.

For summary tables, the descriptive statistics will be rounded to 1 more digit than the individual values for the arithmetic mean, SD, median and geometric mean, and to the same number of digits for the minimum and maximum values. The t_{max} will be reported using the median and range up to 2 decimal points in listing and summary tables. The number of non-

missing observations (n) will be reported as an integer number. The CV% and geometric CV% will be reported as a percentage of the integer number.

For individual plots, the time course of RVT-1401 serum concentration profile will be presented as 1 plot per graph and as composite plots (consisting of overlaid profiles for all subjects with the same dose as connected lines). The graphical output will be presented in both linear and semi-log scales. Actual sampling times will be used for individual plots. For mean plots for each dose group, the arithmetic mean of RVT-1401 serum concentration time profiles will be presented in linear and semi-log graphs. Linear mean plots will be presented with their upper SD bars. Scheduled (nominal) sampling times will be used for mean plots.

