### **3.2.3.2. Pharmacokinetics**

RVT-1401 exhibited non-linear pharmacokinetics (PK) following single SC administration across doses ranging from 0.5 mg/kg to 765 mg. The non-linearity is consistent with RVT-1401 exhibiting target mediated disposition PK. In addition to single dose administration, RVT-1401 has also been administered weekly SC for 4 weeks at doses of 340 and 680 mg. The observed mean concentration-time profile following the first and last dose were generally similar, rising to peak concentration between 2 and 3 days after the dose and then declining beginning 4 days after administration up until the next dose. The rate of elimination was more rapid following administration of 340 mg compared to 680 mg, indicative of target mediated drug disposition. Across both dosing cohorts there was accumulation in the exposure measures of Cmax and AUC(0-168). The accumulation in Cmax and AUC(0-168) in the 340 mg cohort was 7 and 8.7-fold respectively between the first and last dose, and 2.23 and 2.64, respectively in the 680 mg cohort. There was large variability in Cmax and AUC(0-168) after the first dose of 340 mg, whereas there was less variability following first SC dose of 680 mg, consistent with what was observed in single dose data. Overall there was reduction in the inter-individual variability around Cmax and AUC(0-168) after subsequent doses. Following the last dose in the 680 mg cohort, the profile shows characteristics of target mediated drug disposition, with a linear elimination phase from ~96 hours to 168 hours after the last dose, at which time the elimination was very rapid from 168 hours to 336 hours post dose. Exposures increased more than dose proportionally when comparing week four of the 340 mg dose to exposures following the 680 mg SC dose.

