## 4. OBJECTIVE(S) AND ENDPOINT(S)

Objectives	Endpoints
Primary	
To assess the safety and tolerability of RVT-1401 in AChR antibody positive MG patients over a 6-week treatment period	Assessment of safety and tolerability by analysis of AE data and changes from baseline in vital signs, clinical laboratory values, and electrocardiograms
To examine the effects of RVT-1401 on total IgG, IgG subclasses (1-4) and anti-AChR-IgG levels	Change from baseline in levels of total IgG and IgG subclasses (1-4) Change from baseline in levels of anti-AChR-IgG
Secondary	
To examine RVT-1401 PK following repeat doses in patients with Myasthenia Gravis (MG)	PK Parameters of AUC (0-168 h) and maximum concentration (Cmax) after first and last dose  Concentration of RVT-1401 pre-dose (Ctrough)
To measure anti-RVT-1401 antibodies following repeat doses in patients with MG and assess any potential impact on PK or PD	Immunogenicity determined by change from pre-dose in anti-RVT-1401 antibodies, characterization of any anti-RVT-1401 to confirm neutralization potential
To examine the effects of RVT-1401 on the Quantitative Myasthenia Gravis (QMG) score	Change from baseline in the QMG Score
To examine the effects of RVT-1401 on the proportion of patients with improvement on the QMG score by $\geq 3$ points from baseline	Proportion of participants with an improvement on the QMG score by $\geq 3$ points from baseline
To examine the effects of RVT-1401 on Myasthenia Gravis-Activities of Daily Living score (MG-ADL)	Change from baseline in the MG-ADL score
To examine the effects of RVT-1401 on the proportion of participants with an improvement on the MG-ADL Score by $\geq 2$ points	Proportion of participants with an improvement on the MG-ADL Score by $\geq 2$ points

To examine the effects of RVT-1401 on the Myasthenia Gravis Composite (MGC) score	Change from baseline in the MGC score
To examine the effects of RVT-1401 on the proportion of participants with an improvement on the MGC Score by $\geq 3$	Proportion of participants with an improvement on the MGC Score by $\geq 3$ points
To examine the effects of RVT-1401 on the Myasthenia Gravis Quality of Life (MG-QOL15r) score	Change from baseline in the MG-QOL15r score

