Quantitative Myasthenia Gravis (QMG) Score 	X	X			X	X	X	X				X	X		X	X			X	

	Screening 	Treatment Period Week 1 (Days)			Treatment Period Weekly Visit (Weeks)				Treatment Period Week 6 (Days)			Follow-up Period Weekly Visit (Weeks)							Early Withdrawal Visit		
		Day 1 (Baseline)	Day 3	Day 5	2 (Day 8)	3 (Day 15)	4 (Day 22)	5 (Day 29)	6 (Day 36)	Day 38	Day 40	7	8	9	10	12	14	16	18		
Study Timepoint (Weeks)	Within 21 Days																				
Time Window (days)			+1 day	+1 day	+/-1 day	+/-1 day	+/-1 day	+/-1 day	+/-1 day	+1 day	+1 day										
Myasthenia Gravis Composite (MGC) Score 		X			X	X	X	X				X	X			X	X			X	X
Myasthenia Gravis Quality of Life (MG- QOL15r) Score 		X						X				X				X	X			X	X
Satisfaction Questionnaire												X									X
Adverse events	X	X	X	X	X	X	X	X	X	X	X	X	X	X	X	X	X	X	X	X	
Concomitant medication	X	X	X	X	X	X	X	X	X	X	X	X	X	X	X	X	X	X	X	X	

1. Screening can take place over multiple days to ensure participants withhold cholinesterase inhibitors for at least 12 hours prior to the QMG and MGC assessments.
2. Vitals, ECG and blood draws for safety, PK, and PD assessment will be collected pre-dose on dosing days where specified.
3. Pregnancy tests will be collected pre-dose (via urine dipstick) on dosing days where specified. Serum pregnancy tests should be collected at screening, week 18, and early withdrawal.
4. Participants positive for anti- RVT-1401 antibody at Week 18 will be requested to return at approximately 6, 9, and 12 months post-dose for additional samples or until their result is no longer positive. However, for purposes of safety follow-up and database lock participation ends at the Week 18 visit.
5. Local injection site reactions will be assessed at approximately 10 minutes post dose.
6. MG assessments will be assessed pre-dose when collected on dosing days
7. Subjects should be instructed to withhold cholinesterase inhibitors for at least 12 hours prior to the QMG and MGC assessments.

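### SAP 11 treats a BLQ concentration between two quantifiable values as missing even across a new dose, so an isolated BLQ trough is dropped and the mean trough is biased upward by an amount the documents do not let us compute

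*SAP*

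**What the plan says.** In its summary statistics and mean plots, SAP 11 gives a BLQ value a default of zero. The exception reads: "except when an individual BLQ falls between 2 quantifiable values, in which case it will be treated as missing data". Such a value does not enter the mean profile. The rule does not distinguish pre-dose from post-dose samples and does not say that the two neighbours must belong to the same dosing interval.

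Protocol 8.1 (table note 2) fixes the timing: "Vitals, ECG and blood draws for safety, PK, and PD assessment will be collected pre-dose on dosing days where specified". Every PK sample on a dosing day after Day 1 is therefore a trough. Ctrough is a secondary endpoint in Protocol 4, and SAP 11 adds that it "will be determined for every dosing interval (Week 2, Week 3, Week 4, and Week 5"), besides the values after the first and last dose.

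SAP 11 asks for the number and percentage of BLQ values beside the concentration summaries, individual listings and plots, and a geometric mean for Ctrough. It plans no PK inference. It splits the PK analysis into a primary and an OLE section without saying which series of samples the BLQ rule scans.

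**The concern.** Within a single-dose profile, a BLQ value between two quantifiable ones is suspicious, and setting it to missing is defensible. In repeat dosing the next sample may follow another dose. A low trough followed by a higher value can then be real pharmacology, not an assay fault.

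Under the rule as written, whether a given trough enters the mean depends on a result obtained after a later dose. The values removed are by construction the lowest, so the mean that remains is too high. The median and minimum can also move upward, because they are taken on the reduced set.

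Protocol 3.2.3.2 indicates where this is likeliest. Elimination was faster at 340 mg than at 680 mg, first-dose exposure at 340 mg was highly variable, and the accumulation in Cmax and AUC(0-168) "in the 340 mg cohort was 7 and 8.7-fold respectively between the first and last dose", against 2.23 and 2.64 at 680 mg. Early 340 mg troughs are thus the lowest relative to what follows. At stake is a fair description of trough exposure by dose, in a study whose data are meant to support later dose selection (Protocol 3.2.2).

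**Working it through.** **Which samples the exception can reach.** Protocol 8.1 schedules double-blind PK samples on Days 1, 3, 5, 8, 15, 22, 29, 36, 38 and 40 and at Weeks 7 and 8. The Day 1 sample precedes any drug, so Day 3 has no quantifiable value before it. Week 8 is the last scheduled PK sample without the OLE. That leaves nine samples that can lie between two quantifiable values: Days 5, 8, 15, 22, 29, 36, 38 and 40, and Week 7. Five of them (Days 8, 15, 22, 29 and 36) are pre-dose troughs, and Week 7 is an end-of-interval sample.

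**Example.** A participant is quantifiable on Day 5, BLQ on Day 8 and quantifiable on Day 15. The Day 8 trough is dropped. The Day 15 value that triggers this was measured after the Day 8 dose.

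**Size: the documents state no figure.** They give no LLOQ, trough values or BLQ rate. The arm size is 7 (14 active in two arms, 7 placebo, 1:1:1; Protocol 10.1 and 5.3). Let k of 7 troughs be BLQ and dropped, and let the rest have mean M. The rule reports M.

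- If the dropped values are counted as zero, the mean is (7-k)M/7, so the ratio is 7/(7-k). For k = 1, 2, 3: 7/6 = 1.17, 7/5 = 1.40, 7/4 = 1.75.
- If each dropped value is as high as it could be, namely the LLOQ, and M = 5 x LLOQ (assumed), the ratio is 5 / {[(7-k) x 5 + k]/7} = 35/(35-4k). For k = 1, 2, 3: 35/31 = 1.13, 35/27 = 1.30, 35/23 = 1.52.

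**Bias against the true mean, in assumed scenarios.** This was simulated with 100,000 sets of 7. The Day 8 trough was lognormal with a CV of 50%, 100% or 150%, the preceding sample was taken as quantifiable, and the next trough was a fixed multiple of the Day 8 value.

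| Share of Day 8 troughs BLQ | SAP rule, 3- to 8.7-fold rise | SAP rule, 1.5-fold rise |
|---|---|---|
| 5% | +3% to +5% | about +3% |
| 15% | +10% to +15% | about +6% |
| 30% | +20% to +34% | about +7% |
| 50% | +31% to +65% | -1.9% to +0.8% |

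In the last cell the BLQ values that stay at zero offset those dropped. Across all scenarios, setting every BLQ to LLOQ/2 gave a bias of 0% to -10%, and setting every BLQ to zero gave -0.3% to -32%.

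**Runs.** If Days 8 and 15 are both BLQ, a literal reading of the rule (an individual BLQ) leaves both at zero; another reading drops both. On the literal reading, a participant with two low troughs is kept as zero while one with a single low trough is removed.

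**The case against.** The strongest reply is that this may never happen. Lower early troughs at 340 mg need not be below the LLOQ, and Protocol 3.2.2 suggests that full receptor occupancy may not be lost within the dosing interval. The statement that "at which time the elimination was very rapid from 168 hours to 336 hours post dose" concerns the period after the last 680 mg dose, not a 168 h trough during weekly dosing. This stands: a reader might infer that BLQ troughs are the expected pattern here, and the documents do not establish that.

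Other tempting inferences also go too far:

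- *Accumulation is understated.* The optional ratios in SAP 11 use Cmax and/or AUC(0-t) from individual non-compartmental analysis. The BLQ rule covers only descriptive statistics and mean figures, so these ratios are untouched.
- *Loss of exposure is hidden.* BLQ counts and percentages, listings and individual plots give partial disclosure. The mean and mean plot remain affected.
- *OLE and non-OLE participants are treated differently at Week 8.* That follows only if the samples are read as one continuous series; a Week 8 BLQ would then be dropped in an OLE participant quantifiable at Weeks 7 and 9. If each analysis section is scanned separately, Week 8 ends one series or begins the other and counts as zero. The SAP does not say which, so this is an ambiguity and not a demonstrated inconsistency.
- *Every BLQ should simply be zero.* That biases means downward and makes the Ctrough geometric mean incalculable.

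The multipliers against zero are upper bounds, since true values lie between zero and the LLOQ. PK is also secondary and descriptive. None of this answers the central point that the rule lets a later dose decide whether a trough is counted.

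**Conclusion.** The point holds as a minor one. The rule lacks a dosing-interval limit, and where an isolated trough is BLQ between quantifiable neighbours it is dropped and the mean trough is raised. This is most plausible for early 340 mg troughs.

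The size is unknown and is zero if no trough is BLQ. The multipliers assume 7 evaluable participants per arm and 1 to 3 dropped values at the same visit; the simulated biases also rest on the assumed distribution, BLQ share and rise between troughs. With a small rise and many BLQ values the net bias can be about nil.

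The effect is confined to descriptive concentration and Ctrough summaries and mean plots. Individual Cmax and AUC, and the IgG endpoints, are not affected.

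**What to change.** In SAP 11:

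1. Restrict the missing rule to a BLQ between two quantifiable samples within the same dosing interval.
2. Keep every BLQ trough or end-of-interval sample after the first dose in the summaries at one fixed value, whatever follows it. LLOQ/2 is preferable: it had the smaller bias in the scenarios above, allows the Ctrough geometric mean, and matches the halving that SAP 10.2 already applies to laboratory results reported as less than a limit. Report zero as a sensitivity.
3. Apply the same rule to runs of BLQ values, and to the Week 8 sample in OLE and non-OLE participants alike.

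The cost is a few sentences and one programming rule, with no new samples. Mean troughs may come out slightly lower than under the current rule.

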12. PHARMACODYNAMIC ANALYSES

Pharmacodynamic endpoints (total IgG, IgG1, IgG2, IgG3, IgG4, and anti-AChR-IgG level) will be summarized descriptively and analyzed using an ANCOVA model. Descriptive statistics (sample size, mean, standard deviation, median, Q1, Q3, minimum and maximum) of baseline, post-baseline, change from baseline, and percentage change from baseline values for each PD endpoint will be provided by treatment group for all scheduled visits.

The ANCOVA model with treatment as a fixed factor, and baseline value as covariate will be used to produce least-squares means and 95% CIs for each treatment group at each scheduled visit. For each scheduled visit, the least-squares means will be compared using a t-test. Line plots of the least squares means and 95% CIs by visit will also be provided.

There will be no adjustments for multiple comparisons of PD endpoints. An alpha level of 0.05 will determine statistical significance. Analyses of PD endpoints will be provided for the PD analysis population.

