5. GENERAL CONSIDERATIONS FOR DATA ANALYSES

Data will be listed and summarized. Listings will be sorted by treatment, participant, day, and time and include both scheduled and unscheduled visits; table summaries will be presented by treatment include placebo, RVT-1401 340 mg, RVT-1401 680 mg, combined RVT-1401 group, and by scheduled visit.

Open label extension period will start from the date of the first OLE dose for each subject. Unless otherwise specified, data collected during OLE period will be included in the same listings, tables, and figures with data collected during double-blind period.

Unless stated otherwise, descriptive summaries for continuous variables will include n, mean, standard deviation (SD), median, first and third quartiles (Q1, Q3), minimum, and maximum. The geometric mean with associated 95% confidence interval (CI) and the between-participant coefficient of variation (CV) (%CVb) for PK parameters only will also be included. For categorical variables, n and percent will be used as summary statistics. Baseline is the last available assessment prior to time of the first dose unless it is specified otherwise. If there are multiple assessments collected on the same scheduled time, the average of these assessments will be used. For tabulated safety summaries, only the scheduled assessments will be included in the summary tables.

In general, summary statistics for raw variables will be displayed as follows: minima and maxima will be displayed to the same number of decimal places as the raw data. Means, medians, and quartiles will be presented to 1 more decimal place than the raw data ; standard deviations will be presented to 2 more decimal places than the raw data.

The numbers of decimal places for summary statistics of derived variables (i.e., variables that are not measured by the study site but are calculated for analysis based on other measured variables) will be determined on a case by case basis.

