5.1. Analysis Populations

In accordance with guidance from the International Conference on Harmonisation of Technical Requirements for Registration of Pharmaceuticals for Human Use (ICH) *Statistical Principles for Clinical Trials E9* (1998), the following analysis populations will be used for all statistical analyses:

- The full analysis set (FAS) includes all randomized subjects who receive at least one dose of randomized study medication with at least one valid post-treatment value. The FAS is used for all efficacy analyses.
- The per-protocol set (PPS) includes all FAS subjects who do not have significant protocol violations, where a significant protocol violation is one that has the potential to affect analysis conclusions. Final determinations of significant protocol violations will be made at the final blinded data review meeting in accordance with guidance from ICH E9 (Statistical Principles).
- The safety analysis set (SAF) includes all subjects who received at least one dose of study medication. The SAF is used for all safety analyses.

- The Pharmacokinetic (PK) analysis set includes all subjects who undergo PK sampling and have evaluable concentration-time data for analysis.
- The Pharmacodynamic (PD) analysis set includes all subjects who received at least 1 dose of study medication and have a baseline PD measurement and at least 1 post-baseline PD measurement.
- The Open-label Extension (OLE) analysis set includes all subjects who enroll in the OLE study phase and receive at least 1 dose of study medication in the OLE. The OLE subjects will be summarized by actual treatment in the double-blind treatment period for safety and PK analyses and by randomized treatment assigned in the double-blind treatment period for other analyses based on the OLE population.

Solely to understand the influence of dropouts on study conclusions, the FAS will be partitioned into completers and dropouts.

Efficacy analysis will be done as randomized. Safety analysis will be done as treated. In the event the administered dose level is not consistent throughout the double-blinded period, the as treated arm will be determined by the highest dose level received during the double-blinded treatment period.

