A summary of the number and percent of subjects in each analysis set will be provided by treatment group and in total. Analysis based on a 12-week Follow-up analysis set may be provided depending on the number of subjects who choose not to enroll in the OLE study phase.

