5.3. Subject Groups

For analyses based on the SAF analysis set or the PK analysis set, subjects will be grouped for analyses according to the actual treatment received. For all other analyses, subjects will be grouped for analyses according to randomized treatment assignment from the double-blind treatment period.

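### SAP 12 tests IgG and anti-AChR-IgG between randomised arms at every visit with no stop at the first OLE dose, so the Week 9-18 p-values estimate neither drug versus placebo nor persistence off drug

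*SAP*

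**What the plan says.** SAP 12 covers total IgG, IgG1-4 and anti-AChR-IgG. The model is an ANCOVA with treatment and baseline, fitted visit by visit: "For each scheduled visit, the least-squares means will be compared using a t-test". There is no multiplicity adjustment, and "An alpha level of 0.05 will determine statistical significance". The set is the PD set: "Analyses of PD endpoints will be provided for the PD analysis population". Its definition in SAP 5.1 needs one dose, a baseline value and one later value; it has no limit to the double-blind period.

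Two general rules then apply:

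- SAP 5: "Unless otherwise specified, data collected during OLE period will be included in the same listings, tables, and figures with data collected during double-blind period". The same section says "table summaries will be presented by treatment include placebo, RVT-1401 340 mg, RVT-1401 680 mg, combined RVT-1401 group, and by scheduled visit".
- SAP 5.3, for everything except safety and PK: "subjects will be grouped for analyses according to randomized treatment assignment from the double-blind treatment period".

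The SAP does have OLE tools. SAP 5.1 defines an OLE set, grouped "by randomized treatment assigned in the double-blind treatment period for other analyses based on the OLE population", and SAP 5.2 defines an OLE baseline. For those who decline the OLE, "Analysis based on a 12-week Follow-up analysis set may be provided depending on the number of subjects who choose not to enroll" in it. SAP 12 refers to none of these.

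In the protocol, Section 10.3.5 compares each active arm with placebo on PD by ANCOVA at 0.05, also without an end visit. The part headed *OLE and Follow up Analyses* (after 10.3.6) asks for separate, descriptive reporting of the OLE and 12-week follow-up populations. It allows ad hoc tests at Weeks 8, 10 and 12 for information only. SAP 14 does not mention the point.

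**The concern.** Everyone who completes double-blind treatment may take open-label RVT-1401 340 mg every 2 weeks from Week 8 (Protocol 5.1 and 6.4). PD samples on dosing days are drawn before the dose (Protocol 8.2, footnote 4), so Week 8 is the last visit without OLE drug. From Week 9 the arm labelled placebo can contain treated participants. Each active arm can contain some who were re-dosed and some who were not.

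A test by randomised arm then compares assigned sequences with an optional extension. That contrast can be computed, but it is not the question in SAP 8, which is superiority over placebo. It does not measure how long the effect lasts off drug either, because the re-dosed participants are not off drug. Its size depends on how many in each arm chose the OLE.

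IgG and anti-AChR-IgG are primary endpoints in Protocol 4, and Protocol 3.2.2 says that the study data will support dose selection. By-visit least-squares means with confidence intervals and p-values will naturally be read as evidence on durability.

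**Working it through.** The documents give no figure for a between-arm difference after Week 8, so there is none to reproduce. The only planning figure for IgG is the 33-point difference at Week 7, and nothing below rests on it.

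**1. Tests affected.** Visits run weekly to Week 10 and then every 2 weeks to Week 18 (SAP 1.2). After the first OLE dose these are Weeks 9, 10, 12, 14, 16 and 18, which is 6 visits. As far as the extracted tables can be read, total IgG and anti-AChR-IgG are sampled at all of them.

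6 visits x 2 analytes x 2 doses versus placebo = 24 tests.

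This is a minimum. It leaves out late subclass samples and any test of the combined RVT-1401 group, which SAP 12 does not specify.

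**2. Inputs for total IgG** (Protocol 3.2.2 unless stated)

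- On-treatment reduction: 75-80% for 680 mg, 65-70% for 340 mg.
- Off drug: back to baseline 6 to 8 weeks after the sixth dose.
- Active participants in the OLE: trough IgG 15-25% above nadir. Whether this means points of baseline or is relative to nadir is not stated.
- Placebo participants who switch: 35-45% reduction after the last OLE dose.
- Placebo participants not dosed: about 0 (Protocol 3.2.3.3 reports minimal change).
- 7 per arm (21 participants, 1:1:1). OLE uptake is not stated and is varied below.

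**3. Shift of the placebo mean**, with k of 7 switching: (k/7) x 35 to (k/7) x 45.

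- k = 1: 5.0 to 6.4 points
- k = 4: 20.0 to 25.7 points
- k = 7: 35 to 45 points

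**4. Active reduction in the OLE**

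- Points reading: 680 mg, 75 - 25 = 50 to 80 - 15 = 65. 340 mg, 65 - 25 = 40 to 70 - 15 = 55.
- Relative reading: 680 mg, 100 - 25 x 1.25 = 68.75 to 100 - 20 x 1.15 = 77.0. 340 mg, 100 - 35 x 1.25 = 56.25 to 100 - 30 x 1.15 = 65.5.

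**5. Contrast near Week 14**, two weeks after the last OLE dose at Week 12. The sixth dose is on Day 36 and Week 14 is Day 13 x 7 + 1 = 92, so (92 - 36)/7 = 8 weeks have passed and undosed active participants are taken as back at baseline.

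Contrast = (kA/7) x active OLE reduction - (kP/7) x placebo OLE reduction, where kA and kP are the numbers entering the OLE. A positive value means lower IgG on active. The low end pairs the smallest active reduction with 45, the high end the largest with 35.

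| Uptake (kA, kP) | 680 mg, points | 680 mg, relative | 340 mg, points | 340 mg, relative |
|---|---|---|---|---|
| 0, 0 | about 0 | about 0 | about 0 | about 0 |
| 4, 4 | 2.9 to 17.1 | 13.6 to 24.0 | -2.9 to 11.4 | 6.4 to 17.4 |
| 7, 7 | 5 to 30 | 23.8 to 42.0 | -5 to 20 | 11.3 to 30.5 |

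Unequal uptake moves the result further. For 680 mg on the points reading, kA = 7 and kP = 4 gives 50 - 25.7 = 24.3 to 65 - 20 = 45.0. Reversed, kA = 4 and kP = 7 gives 28.6 - 45 = -16.4 to 37.1 - 35 = 2.1.

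With the same drug and the same forecasts, the tested contrast changes size and can change sign with uptake alone.

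**The case against.** **The pooling sentence in SAP 5 is a display rule.** It speaks of listings, tables and figures, so applying it to the ANCOVA data is an inference. That is fair. But SAP 12 itself asks for a test at each scheduled visit in a set with no period limit, and that is enough to produce the Week 9-18 tests.

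**The SAP already provides for OLE analyses.** It has the OLE set and the OLE baseline, and SAP 5.4 mentions OLE endpoints. None of these limits SAP 12. Elsewhere the SAP does draw the line: SAP 11 splits PK into primary and OLE parts, SAP 10.1.6 splits adverse events by period, and SAP 9.4.1 stops the clinical scores at Week 7.

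**SAP 12 only implements the protocol.** This stands in part. Protocol 10.3.5 sets no end visit either, and the information-only sentence follows the ad hoc tests and does not clearly govern that ANCOVA. A reader might infer a plain breach of the protocol; the text does not go that far. The conflict is with the separate, descriptive reporting that the protocol asks for in the OLE and follow-up periods.

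**The late tests understate the drug.** A reader might infer this by setting 5-30 points near Week 14 against 75-80 points on treatment. The documents do not support it. The protocol forecasts a return to baseline 6 to 8 weeks after the sixth dose, so without any OLE the contrast would be about 0 by then. Against that benchmark, full uptake raises the 680 mg contrast. Nor is the end of weekly dosing specific to Week 9: the last weekly dose is at Week 6. What is new from Week 9 is OLE dosing, in the placebo arm and in part or all of the active arms.

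**No decision rests on these tests.** For the Week 7 analysis this is correct and limits the weight of the point.

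**Conclusion.** The point holds and should be fixed. Followed as written, SAP 12 gives at least 24 between-arm p-values for total IgG and anti-AChR-IgG at Weeks 9-18, judged at 0.05, that estimate neither the randomised drug-versus-placebo effect nor its persistence off drug.

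For total IgG each placebo switcher moves the placebo mean by 5.0-6.4 points after the last OLE dose. The net effect on the contrast has no fixed direction. These sizes rest on the protocol's forecasts, 7 per arm, assumed OLE uptake, no change in undosed placebo participants, and full washout in undosed active participants by Week 14. No forecast is given for anti-AChR-IgG or for the contrast at Weeks 9-12. By Week 18 the shift fades, since IgG is forecast to return to baseline 6 to 8 weeks after OLE dosing ends.

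A reader might also infer that the primary result is compromised. It is not: the Week 7 analysis and the ordered hypotheses of SAP 9.2 use data from before the OLE. Summarising later visits by prior arm is not a fault in itself; the fault is the unlabelled test.

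**What to change.** - In SAP 12, limit between-arm PD tests to visits up to and including the Week 8 pre-dose sample.
- Report later visits descriptively and in separate outputs: the OLE set by prior arm, with the OLE baseline of SAP 5.2, and the participants who did not enter the OLE. Label any test there informational. Comparisons within either group are not randomised, because membership is chosen after randomisation.
- The protocol lists Week 8 among its ad hoc visits, so say that the Week 8 test in the PD set falls under Protocol 10.3.5. List any remaining departure in SAP 14.
- Minor alignment: SAP 9.4.2 summarises responders at all timepoints and then names Fisher's exact test. State that these between-arm tests use no data after the first OLE dose, in line with the Week 7 endpoints of SAP 9.4.1.

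The cost is SAP wording and small changes to table and figure shells. No new data are needed: the Week 8 samples are already drawn before dosing, and the OLE set and baseline already exist. The price is that there are no formal between-arm PD p-values after Week 8.
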